6.1.7.3 Grade 3 or 4 Adverse Events or Serious Adverse Events

If a subject experiences a Grade 3 or 4 adverse event or a serious adverse event that the investigator considers to have a reasonable possibility of relationship to study drug, the investigator should assess whether the adverse event can be managed medically without interruption of study drug, or whether study drugs should be interrupted until it improves.

If study drugs are interrupted and restarted and the adverse event recurs, then study drugs should be permanently discontinued.

If a subject experiences a Grade 3 or 4 adverse event or serious adverse event that is considered unrelated (no reasonable possibility) to the study drugs, it is not necessary to interrupt study drugs unless an interruption is required because of the nature of the event (e.g., unable to take oral medications).

The investigator should ensure that all serious adverse events are reported to AbbVie within 24 hours of awareness. Serious adverse event follow-up information, including associated dose interruptions (or discontinuations), must be reported to AbbVie within 24 hours of awareness by entering updated SAE information into the appropriate eCRFs.

Grade 3 or 4 adverse events and any associated dose interruptions (or discontinuations) should be entered into the appropriate eCRFs.

6.1.7.4 Management of Decreases in Hemoglobin for Subjects Receiving RBV

Reductions in hemoglobin are a well characterized side effect of RBV exposure. If a subject experiences a hemoglobin decrease that meets the criteria outlined in [Table 13](#), a confirmatory test should be performed. If the hemoglobin decrease is confirmed to meet the criteria, the management guidelines in [Table 13](#) should be followed, unless local RBV label requires a more stringent management. Management will be different for subjects without a history of known cardiac disease and subjects with known cardiac disease.

Use of hematologic growth factors (such as erythropoietin, filgrastim), or blood transfusions is not recommended and is permitted only with approval of the AbbVie Study TA MD. Management of hematologic growth factor therapy is the responsibility of the investigator, and growth factors will not be provided by AbbVie.

Alternate management of hemoglobin decreases outside of these criteria requires approval of the AbbVie Study TA MD, except for more stringent management requirement from a local RBV label.

Table 13. Management of Hemoglobin Decreases

Hemoglobin Reduction in Patients Without Cardiac Disease or History of Cardiac Disease	
Hemoglobin < 10.0 g/dL, but ≥ 8.5 g/dL	Study drugs may be continued
	Reduce RBV dose to 600 mg QD* and continue to monitor hemoglobin levels per protocol
	If hemoglobin increases to ≥ 10 g/dL, may increase RBV, with gradual dose increases in 200 mg increments towards original dose
	If Hb decreases to < 8.5 g/dL see appropriate row below
	Enter discontinuation into appropriate eCRFs and create corresponding adverse event
Hemoglobin < 8.5 g/dL	Permanently discontinue RBV and manage the subject as medically appropriate
	Enter discontinuation into appropriate eCRFs and create corresponding adverse event
Reduction in Patients with Stable Cardiac Disease or History of Stable Cardiac Disease	
Hemoglobin decrease of ≥ 2 g/dL during a 4-week treatment period (Hemoglobin ≥ 10 g/dL)	Study drugs may be continued
	Reduce RBV dose to 600 mg QD* and continue to monitor hemoglobin levels per protocol
	If a subsequent hemoglobin result is greater than the level that triggered the dose reduction, the investigator may elect to increase RBV, with gradual, 200 mg dose increases towards the original dose
	If the subject has symptoms consistent with their cardiac disease, manage subject as medically appropriate and AbbVie Study TA MD may be contacted
	If hemoglobin does not increase, investigator may manage the subject as medically appropriate. If hemoglobin decreases to < 10 g/dL see appropriate row below
Hemoglobin < 10.0 g/dL, but ≥ 8.5 g/dL	Study drugs may be continued
	Continue at reduced RBV dose as above (or reduce RBV dose to 600 mg QD* if this is the initial reduction) and continue to monitor hemoglobin per protocol
	If hemoglobin increases to ≥ 10 g/dL, may increase RBV; with gradual dose increases in 200 mg increments towards original dose
	If hemoglobin < 10 g/dL despite being for 4 weeks on the reduced RBV dose, permanently discontinue RBV and manage the subject as medically appropriate
Hemoglobin < 8.5 g/dL or < 12 g/dL after 4 weeks of dose reduction	Permanently discontinue RBV and manage the subject as medically appropriate
	Enter discontinuation into appropriate eCRFs and create corresponding adverse event

* For subjects aged 12 to less than 18, RBV dose reduction should be per local RBV label.

Management of other hematologic parameters besides hemoglobin (like WBC, platelets, neutrophils, etc.) should be performed according to the local RBV label. Alternative RBV dosing can be used if agreed upon by AbbVie TA MD.

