6.1.7 Toxicity Management

For the purpose of medical management, all adverse events and laboratory abnormalities that occur during the study must be evaluated by the investigator. All adverse events and laboratory abnormalities will be managed and followed to a satisfactory clinical resolution. A toxicity is deemed "clinically significant" based on the medical judgment of the investigator. Please refer to Section 6.1.7.1, Section 6.1.7.2, Section 6.1.7.3, Section 6.1.7.4, Section 6.1.7.5, and Section 6.1.7.6 for details on Toxicity Grades.

Interruption of DAA therapy is not recommended, and if interruption occurs under extenuating circumstances (e.g., due to hospitalization of the subject), it should be less than 7 consecutive days. If study drug interruption lasts for longer than 7 days, the investigator should contact the AbbVie Study TA MD. The Investigator should ensure that any study drug interruptions or RBV dose modifications and associated adverse events are promptly entered into the appropriate eCRFs.

The toxicity management guidelines below should be followed throughout the Treatment Period of the study. Specific toxicity management guidelines apply to the instances of:

decreases in hemoglobin for subjects receiving RBV (Section 6.1.7.4), increases in ALT (Section 6.1.7.5), and reductions in Creatinine Clearance (Section 6.1.7.6).

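### Table 13 gives cardiac subjects two 4-week ribavirin stopping thresholds (<10 and <12 g/dL) with no precedence, and tells sites to record a discontinuation when a non-cardiac subject has only a dose reduction

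*Protocol*

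**What the plan says.** Table 13 in Protocol Section 6.1.7.4 has separate blocks for subjects without and with stable cardiac disease.

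**Cardiac block, three rows.**
- Row 1 (a fall of at least 2 g/dL within 4 weeks, hemoglobin still 10 g/dL or more): reduce ribavirin. If a later value exceeds the one that triggered the reduction, "the investigator may elect to increase RBV, with gradual, 200 mg dose increases towards the original dose". Otherwise, "If hemoglobin does not increase, investigator may manage the subject as medically appropriate".
- Row 2 (8.5 to <10 g/dL): reduce, or stay reduced. Then "If hemoglobin increases to ≥ 10 g/dL, may increase RBV; with gradual dose increases in 200 mg increments towards original dose", but "If hemoglobin < 10 g/dL despite being for 4 weeks on the reduced RBV dose, permanently discontinue RBV".
- Row 3 ("Hemoglobin < 8.5 g/dL or < 12 g/dL after 4 weeks of dose reduction"): permanent discontinuation of ribavirin.

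The surrounding text gives way to a stricter local ribavirin label and adds that "Alternate management of hemoglobin decreases outside of these criteria requires approval of the AbbVie Study TA MD". It does not rank the rows.

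**Non-cardiac block, 8.5 to <10 g/dL row.** Study drugs may continue and ribavirin drops to 600 mg daily, yet the row ends "Enter discontinuation into appropriate eCRFs and create corresponding adverse event". The row below it (<8.5 g/dL), where ribavirin really stops, carries the same line. Section 6.1.7 separately says: "The Investigator should ensure that any study drug interruptions or RBV dose modifications and associated adverse events are promptly entered into the appropriate eCRFs".

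**The concern.** The cardiac rows permit opposite actions on the same hemoglobin value. Two 4-week thresholds carry the same consequence, and the lower one is redundant if the higher one governs, which points to a drafting error rather than a graded scheme. At stake is consistent handling of anemia in the subjects least able to tolerate it: one site could stop ribavirin for good where another raises the dose.

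The recording line matters because the SAP treats the two events differently. SAP Section 8.1 counts subjects who completed all study drugs, subjects who completed the DAAs (including those who stopped ribavirin), and subjects with a ribavirin dose modification. SAP Section 9.2 adjusts the expected number of ribavirin tablets using the RBV Dose Modifications eCRF. A reduction recorded as a discontinuation could misstate the completion count. If nothing reaches the dose-modification form, the modification count is wrong too. Either error can label an adherent subject non-compliant.

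**Working it through.** **Part 1: cardiac rows compared, 4 weeks after the reduction.**

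| Hemoglobin (g/dL) | Row 1 | Row 2 | Row 3 | Result |
|---|---|---|---|---|
| <8.5 | not applicable | stop | stop | agree |
| 8.5 to <10 | refers to row 2 | stop | stop | agree |
| 10 to <12 | may increase, or discretion | may increase | stop | conflict |
| 12 or more | may increase, or discretion | may increase | no stop | agree |

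The conflict is confined to 10 to <12 g/dL. Subjects can be in that band from entry, because exclusion criterion 12 removes only those below 10 g/dL unless the local label is stricter. Example: a subject enters at 11, falls to 9.5, is reduced, and reads 10.5 after 4 weeks. Row 2 allows an increase; row 3 requires permanent discontinuation.

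Ribavirin weeks governed by the choice, using scheduled hematology only (Appendix C: Weeks 2, 4, 8, Week 12 in Arm B, and end of treatment):
- Reduction at Week 2 or 4: the first scheduled value at least 4 weeks later is Week 8. Remaining in Arm B: 16 − 8 = 8 of 16 weeks (50%). Remaining in Arm A: 12 − 8 = 4 of 12 weeks (33%).
- Reduction at Week 8, Arm B: check at Week 12, leaving 16 − 12 = 4 of 16 weeks (25%).

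**Part 2: effect of the recording line on compliance.**

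Inputs: 200 mg tablets (Protocol Section 5.5.1), so 1200 mg = 6, 1000 mg = 5 and 600 mg = 3 tablets a day; 112 days in Arm B, 84 in Arm A; compliant range 80% to 120% (SAP Section 9.2). Assumed: full planned duration and perfect adherence.

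Compliance = tablets taken ÷ tablets expected. The expected number depends on what is on the dose-modification form.

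Arm B, 1200 mg reduced to 600 mg after Day 28. Taken = 28×6 + 84×3 = 420.
- Entered as a reduction: expected 420, so 100%.
- Entered as 0 mg: expected 28×6 = 168, so 420/168 = 250%.
- No entry on the form: expected 112×6 = 672, so 420/672 = 62.5%.

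| Other cases | Taken | 0 mg entry | No entry |
|---|---|---|---|
| Arm B, 1200 mg, after Day 84 | 84×6 + 28×3 = 588 | 588/504 = 116.7% | 588/672 = 87.5% |
| Arm B, 1000 mg, after Day 28 | 28×5 + 84×3 = 392 | 392/140 = 280% | 392/560 = 70% |
| Arm A, 1200 mg, after Day 28 | 28×6 + 56×3 = 336 | 336/168 = 200% | 336/504 = 66.7% |

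Early reductions leave the compliant range under either wrong entry. The late one stays inside it. One misclassified subject moves the compliant percentage by 1/5 = 20 points in Arm A or 1/45 = 2.2 points in Arm B.

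**The case against.** The cardiac rules are nested: below 10 g/dL both require stopping. In the disputed band only row 3 is mandatory and keyed to 4 weeks, while the competing options are permissive, so a careful reader can let row 3 override. That reading is reasonable, but the table does not state it. The sponsor-approval rule does not settle the matter, because it covers management outside the criteria and both actions here are inside them. The local-label clause helps only where the label is stricter.

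Exposure is also uncertain. Uncontrolled cardiac disease is excluded, no count of cardiac subjects is given, and confirmatory or unscheduled tests could bring the decision forward. A Week 2 reduction reaches 4 weeks at Week 6. These points stand, and the weeks shown are per affected subject.

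On recording, the documents do not show what a site following the line would enter. Section 6.1.7 points sites to dose modifications. A 0 mg entry would probably still count as a modification, because SAP Section 9.2 treats an interruption as a modification to 0 mg. So the modification count is at risk mainly when nothing is entered on that form; a false discontinuation can still distort the completion count. Tablet counts, monitoring and the per-subject compliance listing may catch the error, and a value of 250% would be conspicuous. Compliance is descriptive and defines no analysis population. All this limits the harm but does not correct the instruction.

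**Conclusion.** Both defects hold in the current table and should be fixed. For cardiac subjects at 10 to <12 g/dL after 4 weeks on reduced ribavirin, the table supports permanent discontinuation, holding or re-escalation. On scheduled visits this governs between a quarter and a half of the planned ribavirin weeks in Arm B, or a third in Arm A for a reduction at Week 2 or 4. The number of subjects affected cannot be derived from the documents.

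For non-cardiac subjects at 8.5 to <10 g/dL, the recording line contradicts the row's own action. If followed literally after an early reduction, it can turn 100% compliance into 250% or 62.5%, assuming full duration and perfect adherence. Confidence is high that the wording is wrong; how often it would mislead a site is unknown. SVR12, its confidence intervals and the sample size are unaffected.

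**What to change.** 1. **Cardiac rows.** State that row 3 overrides rows 1 and 2 once 4 weeks on the reduced dose have passed. Limit the re-escalation and discretion options in rows 1 and 2 to the period before that check, or to hemoglobin of at least 12 g/dL afterwards. Replace row 2's own 4-week sentence with a pointer to row 3. If the clinical team intends 10 g/dL, change the 4-week figure in row 3 from 12 to 10 instead. The documents do not show which was meant, so that choice is clinical.
2. **Non-cardiac 8.5 to <10 g/dL row.** Change the recording line so that sites enter a dose modification, not a discontinuation.

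The cost is a clarification letter or amendment text and an eCRF completion note, with no change to sample size, endpoints or analyses. Keeping 12 g/dL means that more cardiac subjects stop ribavirin than under 10 g/dL.

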6.1.7.5 Management of Increases in ALT

If a subject experiences a post-baseline ALT value $\geq 5 \times$ ULN that is also $\geq 2 \times$ Baseline value, the subject should have a confirmatory test should be performed. If, the ALT is value confirmed $\geq 5 \times$ ULN, and $\geq 2 \times$ Baseline value, the recommendations below should be followed:

- Complete hepatic questionnaire
- Evaluate for alternate etiology of ALT elevation; document in the source, update the medical history and concomitant medications eCRF (if applicable), and obtain Anti-HAV IgM, Anti-HAV Total, Anti-HBc IgM, Anti-HBc Total, Anti-HBs, HBV DNA, HBsAg, Anti-HEV IgM, Anti-HEV IgG and HEV RNA, and other additional tests, as appropriate.
- Manage the subject as medically appropriate.
- Repeat ALT, AST, total and fractionated bilirubin, alkaline phosphatase and INR within 1 week. Repeat liver chemistries as indicated until resolution.
- Discontinue study drugs if any of the following is observed at any time:
 - ALT level is $\geq 20 \times$ ULN in the absence of an alternate etiology.
 - Increasing direct bilirubin or INR or onset of symptoms/signs of hepatitis.
 - At the discretion of the investigator.

Alternate management of confirmed ALT increases requires approval of the AbbVie Study TA MD.

6.1.7.6 Management of Reductions in Creatinine Clearance for Subjects Receiving RBV

Estimated glomerular filtration rate (eGFR, calculated using the MDRD equation) and Creatinine clearance (CrCl, estimated using the Cockcroft-Gault equation) will be calculated throughout the study. Both results will be provided to the investigators, but toxicity management and RBV dose adjustment will be performed based on CrCl values only.

If a subject experiences an CrCl value below 50 mL/min, a confirmatory test should be performed as soon as possible. If CrCl is confirmed to be below 50 mL/min, medical evaluation should include a full review of concurrent medications, including those taken on an as needed basis, those which are sold over the counter, and any dietary and herbal supplements.

In addition, the following should occur:

- Concomitant medication dose reduction based on CrCl or eGFR should be done as per local prescribing information of the concomitant medication (if applicable).
- The AbbVie Study TA MD should be contacted to discuss whether dose modification or drug substitution may be required for concomitant medications given the reduced kidney function as well as potential drug interactions with the DAAs. Drug interactions between concomitant medications and the DAAs, for example, could potentially increase antihypertensive medications' exposures, especially in the setting of reduced kidney function and may result in further deterioration of renal function. Also, if anti-hypertensive medications are adjusted, vital signs must be closely monitored to ensure appropriate blood pressure control.
- The dose of RBV should be adjusted as follows:
 - for CrCl between 30 and 50 mL/min: alternating doses of 200 and 400 mg every other day;
 - for CrCl less than 30 mL/min – 200 mg daily.
- A urine specimen should be obtained for urinalysis (including urine for albumin), and a separate urine specimen for archive should be obtained.
- Creatinine clearance and any other necessary analytes should be repeated within 7 days and as clinically indicated until resolution.
 - If CrCl improves to > 50 mL/min within 14 days after RBV dose modification, consideration should be given to increase RBV dose towards the original value. If CrCl decreases below 50 mL/min again, RBV should be permanently discontinued.

The investigator should ensure that any concomitant medication changes, RBV dose modifications, study drug interruption and study drug discontinuations, as well as related adverse events are entered into the appropriate eCRFs.

Alternative management of RBV dose in the setting of reduced renal function will require approval of the AbbVie Study TA MD, unless it is a more stringent management required by local RBV label.

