5.1.1 Screening

At the Screening Visit, subjects who provide written (signed and dated) informed consent prior to any study specific procedures will receive a unique subject number via the Interactive Response Technology (IRT) system.

The investigator will evaluate whether the subject meets all of the eligibility criteria specified in Section 5.2.1 and Section 5.2.2 during the period from the Screening Visit through Study Day 1 prior to dosing and record the results of this assessment and the details of the informed consent process in the subject's medical records. Eligible subjects have up to 42 days following the Screening Visit to enroll into the study.

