11. Any cause of liver disease other than chronic HCV-infection, including but not limited to the following:
 - Hemochromatosis

- Alpha-1 antitrypsin deficiency
 - Wilson's disease
 - Autoimmune hepatitis
 - Alcoholic liver disease
 - Steatosis or steatohepatitis on liver biopsy considered to be the primary cause of the liver disease rather than concomitant/incidental with HCV infection
12. Screening laboratory analyses showing any of the following abnormal laboratory results:
- ALT > 10 × ULN
 - AST > 10 × ULN
 - Albumin < 2.8 g/dL
 - International normalized ratio (INR) > 1.5, unless subject has known hemophilia or is on a stable anticoagulant regimen affecting INR
 - Hemoglobin < 10 g/dL, or as per local RBV label, if more restrictive.
 - Platelets < 50,000 cells per mm³ for subjects aged ≥ 18 years, or < 40,000 cells per mm³ for subjects aged < 18 years.
 - Calculated creatinine clearance < 30 mL/min
13. History of solid organ transplantation.
14. Receipt of any HCV treatment after failing the treatment regimen in the AbbVie HCV parent study.
15. Discontinuation of the prior HCV treatment in the AbbVie HCV parent study for reasons other than virologic failure (e.g., non-adherence, lost to follow-up, and/or the occurrence of an adverse event).
16. Recent (within 6 months prior to study drug administration) history of drug or alcohol abuse that could preclude adherence to the protocol in the opinion of the investigator.
17. Consideration by the investigator, for any reason, that the subject is an unsuitable candidate to receive ABT-493, ABT-530, SOF, or RBV.

18. Subject who cannot participate in the study per local law.
19. Current enrollment in another interventional clinical study or previous enrollment in this study (except the AbbVie HCV parent study). Concurrent participation in a non-interventional, epidemiologic or registry trials may be permitted with approval by the AbbVie TA SD/TA MD.
20. Subject has confirmation of HCV reinfection at screening visit (as defined in Section 5.4.1.1).

Rationale for Exclusion Criteria

1, 2, 3, 8, 10 – 12, 17 – 19	In order to ensure safety of the subjects throughout the study
6, 7, 13 – 19, 20	In order to avoid bias for the evaluation of efficacy and safety, including concomitant use of other medications
4, 9, 11	To exclude subjects with liver diseases other than HCV
5	To exclude subjects with HIV-2 co-infection

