or non-fasting status will be recorded in the source documents and on the laboratory requisition. The baseline laboratory test results for clinical assessment for a particular test will be defined as the last measurement prior to the initial dose of study drug.

A central laboratory will be utilized to process and provide results for the clinical laboratory tests.

Instructions regarding the collection, processing, and shipping of these samples will be provided by the central laboratory chosen for this study. The certified laboratory chosen for this study is Covance. Samples will be sent to the following addresses:

Covance
[name]
[name]
(For sites in North America)

Covance
[name]
[name]
[name]
(For sites in Europe)

Covance (Asia) Pte Ltd
[name]
[name]
[name]
(For sites in Asia, Australia and New Zealand)

Table 10. Clinical Laboratory Tests

Hematology	Clinical Chemistry	Other Tests
Hematocrit	Blood Urea Nitrogen (BUN)	Anti-HIV Ab ^e
Hemoglobin	Uric Acid	FSH (all females) ^e
Red Blood Cell (RBC) count	Creatinine	Urine and Serum
White Blood Cell (WBC) count	Creatinine clearance (Cockcroft-Gault calculation)	Human Chorionic Gonadotropin (hCG) for females ^f
Neutrophils	eGFR (MDRD method)	HCV RNA
Bands, if detected	Total bilirubin ^a	HIV-1 RNA ^b
Lymphocytes	Direct and indirect bilirubin	Hemoglobin A1C ^e
Monocytes	Serum Alanine Aminotransferase (ALT)	HCV genotype and subtype ^e
Basophils	Serum Aspartate Aminotransferase (AST)	Pharmacogenetic sample (optional)
Eosinophils	Alkaline phosphatase	Alpha2-macroglobulin ^g
Platelet count (estimate not acceptable)	Gamma-glutamyl transferase (GGT)	Haptoglobin ^g
Reticulocyte count	Total protein	Apolipoprotein A1 ^g
Prothrombin Time/INR ^a	Albumin ^a	CD4, CD4% ^b
Activated partial thromboplastin time (aPTT)	Glucose	CD8, CD8% ^b
Urinalysis	Total insulin	CD4:CD8 ^b
Specific gravity	Sodium	Anti-Hepatitis A Virus IgM ^h
Ketones	Potassium	Anti-Hepatitis A Virus Total ^h
pH	Calcium	Anti-Hepatitis E Virus IgG ^h
Protein	Inorganic phosphorus	Anti-Hepatitis E Virus IgM ^h
Blood	Chloride	HEV RNA ^h
Glucose	Bicarbonate	HBsAg ^{e,h}
Urobilinogen	Magnesium	Anti-HBc IgM ^h
Bilirubin	Cholesterol	Anti-HBc Total ^h
Leukocyte esterase	Triglycerides	Anti-HBs ^h
Microscopic (reflex)	Low Density Lipoproteins (LDL) ^{b,c,d}	HBV DNA ^h
Albumin ⁱ	High Density Lipoprotein (HDL) ^{b,d}	

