All screening activities must be completed and reviewed prior to enrollment. Subjects who meet the eligibility criteria will proceed to enrollment via the IRT system on Day 1 (Treatment Period). Subject numbers will be unique 5-digit numbers starting with 10001. The first 3 digits will represent the investigative site and the last 2 digits will represent the subjects screened at that site. Enrolled subjects will keep their subject number throughout the study.

Study Drug Compliance for Kits

Bottles of ABT-493/ABT-530, SOF and RBV will be provided for subject dosing to the site. Each subject will have compliance documented by the site in the subject's source notes for ABT-493/ABT-530, SOF and RBV. At each drug accountability visit in [Appendix C](#), the overall number of tablets of ABT-493/ABT-530, SOF and RBV remaining in each bottle will be recorded in the source and transferred to the IRT system along with the date of reconciliation.

HCV Genotype and Subtype

Plasma samples for HCV genotype and subtype will be collected at Screening. Genotype and subtype will be assessed using the Versant[®] HCV Genotype Inno LiPA Assay, Version 2.0 or higher (LiPA; Siemens Healthcare Diagnostics, Tarrytown, NY). If the LiPA assay is unable to genotype/subtype a sample, its genotype/subtype will be determined by a Sanger sequencing assay of a region of the NS5B gene (Covance).

HCV RNA Levels

Plasma samples for HCV RNA levels will be collected as indicated in [Appendix C](#). Plasma HCV RNA levels will be determined for each sample collected by the central laboratory using the COBAS[®] AmpliPrep/COBAS[®] TaqMan HCV Quantitative Test, v2.0. For this assay, the lower limit of detection (LLOD) and the lower limit of quantification (LLOQ) are both 15 IU/mL.

HCV Resistance Testing Sample

A plasma sample for HCV resistance testing will be collected prior to dosing on Day 1 and at the study visits indicated in [Appendix C](#). Specific instructions for preparation and storage of HCV RNA and HCV resistance samples will be provided by the central laboratory, AbbVie, or its designee.

Archive Serum and Plasma Sample

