5.5 Treatments

5.5.1 Treatments Administered

Each dose of study drug (ABT-493/ABT-530, SOF, and RBV) will be dispensed in the form of tablets at the visits listed in [Appendix C](#). The date and time of dosing will be recorded to the nearest minute in the source documents (or study drug dosing card) and the eCRF for the 2 days immediately prior to each study visit starting prior to the Week 2 visit.

AbbVie will provide ABT-493/ABT-530 as 100 mg/40 mg film-coated tablets. ABT-493/ABT-530 will be taken orally as three tablets QD (total daily dose of 300 mg/120 mg) and with food.

AbbVie will provide SOF as 400 mg tablets. SOF will be taken orally as 1 tablet QD, with food.

AbbVie will provide RBV as 200 mg tablets. RBV dosing is determined based on the age and weight of the subject at the Day 1 visit, as described in [Table 8](#). RBV should be taken

with food. The RBV dose established at Day 1 should be maintained throughout the entire treatment, regardless of ulterior changes in age or weight, unless a dose modification is needed due to toxicity (see Section 6.1.7).

Study drug must not be dispensed without contacting the IRT system. Study drug may only be dispensed to subjects enrolled in the study through the IRT system. At the end of the Treatment Period or at the Premature D/C Visit from the Treatment Period, the site will contact the IRT system to provide visit date information and study drug return information for each kit (Section 5.5.7).

In the event that there is an issue with the study drug supply during the Treatment Period, commercial drug may be provided only with prior AbbVie approval, so that the subject does not experience treatment interruptions. If commercial drug is provided, AbbVie will provide instructions for documentation.

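### A subject known at Screening to have creatinine clearance of 30 to <50 mL/min is eligible, but by default starts ribavirin at 2 to 4 times the protocol's own renal dose

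*Protocol*

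**What the plan says.** **Eligibility.** Among the laboratory exclusions in Protocol 5.2.2 (criterion 12) is "Calculated creatinine clearance < 30 mL/min". Nothing there excludes 30 to <50 mL/min.

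**When the value is known.** Table 10 (Protocol 5.3.1.1) lists "Creatinine clearance (Cockcroft-Gault calculation" among the chemistry results, and Appendix C schedules chemistry at Screening and again on Day 1 before the first dose. Protocol 5.3.1.1 adds: "All screening activities must be completed and reviewed prior to enrollment". On timing, Protocol 5.1.1 says: "Eligible subjects have up to 42 days following the Screening Visit to enroll into the study".

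**Starting dose.** Protocol 5.5.1 states: "RBV dosing is determined based on the age and weight of the subject at the Day 1 visit". Table 8 gives the doses and has no renal row. The Day 1 dose is then kept, "unless a dose modification is needed due to toxicity (see Section 6.1.7".

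**Renal dose.** Protocol 6.1.7.6 requires a CrCl below 50 mL/min to be confirmed promptly. On confirmation ribavirin changes: "for CrCl between 30 and 50 mL/min: alternating doses of 200 and 400 mg every other day". The parent section, 6.1.7, says: "The toxicity management guidelines below should be followed throughout the Treatment Period of the study". Protocol 1.3 starts the Treatment Period on Day 1.

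**The concern.** The protocol names a ribavirin dose for CrCl 30 to 50 mL/min and admits subjects in that range, yets its starting-dose rule does not refer to that dose. A site that follows Table 8 gives such a subject a dose that 6.1.7.6 would cut once the low value is confirmed, although the low clearance was on file before Day 1.

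The hemoglobin rules do not have this gap. Entry requires at least 10 g/dL, and for subjects without cardiac disease the first ribavirin reduction is triggered below 10 g/dL (Table 13). On the Screening value, nobody enters already below the trigger. For CrCl the entry limit is 30 and the trigger is 50.

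What is at stake is avoidable ribavirin exposure in subjects with reduced clearance. Protocol 6.1.7.4 describes falls in hemoglobin as a known effect of ribavirin.

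**Working it through.** **Inputs**
- Adult start: 1000 mg/day (<75 kg) or 1200 mg/day (≥75 kg), Table 8.
- Adolescent start: 600 to 1200 mg/day by weight, Table 8.
- Renal dose at CrCl 30 to 50: 200 mg and 400 mg on alternating days, 6.1.7.6. Mean = (200 + 400)/2 = 300 mg/day.

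If the phrase were read as dosing on alternate days only, the mean would be 150 mg/day and every ratio below would double. The 300 mg reading is the cautious one.

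**Ratio of start to renal dose**
- Adults: 1000/300 = 3.3 and 1200/300 = 4.0.
- Adolescents: 600/300 = 2.0 to 1200/300 = 4.0.

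**Excess per day**
- Adults: 1000 − 300 = 700 mg to 1200 − 300 = 900 mg.
- Adolescents: 600 − 300 = 300 mg to 1200 − 300 = 900 mg.

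**How long the excess lasts.** This depends on which value can trigger 6.1.7.6.

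| Reading | Duration | Adult excess | Adolescent excess |
|---|---|---|---|
| A repeated low Screening value counts as confirmed when Day 1 opens | none | 0 | 0 |
| Low Day 1 pre-dose value confirms the low Screening value | laboratory turnaround | 0.7-0.9 g per day | 0.3-0.9 g per day |
| Day 1 value triggers and a further sample confirms (3-7 days, assumed) | 3-7 days | 3 × 700 = 2.1 g to 7 × 900 = 6.3 g | 3 × 300 = 0.9 g to 6.3 g |
| Week 2 is the first value that counts | 14 days, plus confirmation | 14 × 700 = 9.8 g to 14 × 900 = 12.6 g | 14 × 300 = 4.2 g to 12.6 g |

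The 3-7 days are an assumption, because the protocol sets no number of days for confirmation. They are 3/84 = 3.6% to 7/84 = 8.3% of a 12-week course, and 3/112 = 2.7% to 7/112 = 6.3% of a 16-week course.

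The adolescent upper ends need a weight of at least 75 kg. By the Cockcroft-Gault formula in SAP 7.1, a 17-year-old boy of 75 kg has CrCl below 50 only if creatinine exceeds (140 − 17) × 75/(72 × 50) = 2.6 mg/dL (girl: × 0.85 = 2.2 mg/dL). That is a fringe case.

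**Compliance.** SAP 9.2 adjusts the expected ribavirin tablet count only for changes recorded on the dose-modification eCRF. If a reduced adult start were not recorded there, a fully adherent subject would show 300/1200 = 25% to 300/1000 = 30%, below the 80% limit.

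**The case against.** **The renal rule may already reach these subjects.** Protocol 6.1.7.6 says CrCl is calculated over the whole study and puts no post-baseline limit on its trigger. The ALT rule just before it, 6.1.7.5, does contain that limit. Section 6.1.7 says when the rules are followed, not which values count. A low Screening value that has been repeated could thus be confirmed when the Treatment Period opens. This stands as a possible reading, so it cannot be said that the first dose is unadjusted on every reading. Against it are the section title, which speaks of reductions in subjects already receiving ribavirin, the step-up towards an original dose, and the absence of any pointer from 5.5.1 for the starting dose. The text is ambiguous.

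**A lower start is already possible.** Table 8 is labelled as recommendations, and the line beneath it allows another dose with prior agreement of the sponsor's medical director. Protocol 6.1.7.6 lets a stricter local label prevail. Exclusions 9 and 17 allow the investigator to judge a subject unsuitable, and out-of-range results judged clinically significant are repeated. These make an unconsidered full-dose start less likely, and a reader should not infer that the protocol forces one. But each is discretionary or conditional, and none names a starting dose. An investigator who lowers the dose without that agreement also risks a deviation under Protocol 7.0.

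**A lower dose has a price.** The renal dose cuts adult ribavirin by 700/1000 = 70% to 900/1200 = 75% in a population that Protocol 3.2 calls difficult to cure. That is true, but 6.1.7.6 already accepts this cut once a low value is confirmed.

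**Conclusion.** The concern holds, and the text should be fixed. By default, an eligible subject with known CrCl of 30 to <50 mL/min starts ribavirin at 3.3-4.0 times (adults) or 2.0-4.0 times (adolescents) the mean dose that 6.1.7.6 sets for the same clearance. These ratios rest on reading the renal regimen as 300 mg/day on average.

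The duration is less certain. If the Day 1 sample confirms the Screening value, the excess may last only until the result is back. The 14-day figure is a worst case and should not be read as expected exposure, because it requires the Day 1 pre-dose chemistry to be disregarded.

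A reader might also infer harm to the efficacy result. The documents do not support that: they give no count of subjects in this CrCl range, the number is probably small, and nothing links the starting dose to SVR12 or its analysis. This is a limited, avoidable safety exposure caused by the default dosing text.

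**What to change.** **Table 8 and Protocol 5.5.1.** State that a subject with Screening CrCl 30 to <50 mL/min, confirmed by a repeat before dosing, starts ribavirin on the 6.1.7.6 dose or a more stringent local-label dose, unless the medical director agrees another dose before Day 1. A low Day 1 pre-dose value after a low Screening value counts as confirmation.

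**Protocol 6.1.7.6.** This section assumes a fall during treatment. It allows a step-up towards the original dose if CrCl recovers above 50 within 14 days, and requires permanent discontinuation if CrCl drops below 50 again. Left unchanged, it would give a subject who starts on the renal dose no defined original dose, and could take a stable subject fluctuating around 50 off ribavirin for good. For these subjects, state that the original dose means the Table 8 age/weight dose, that any step-up needs the medical director's agreement, and that a further value below 50 means return to the renal dose, not discontinuation.

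**eCRF.** Record the reduced starting dose so that the SAP 9.2 expected tablet count is correct.

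**Cost.** A short amendment with ethics approval and, where required, regulatory approval (Protocol 9.1); one repeat creatinine sample per affected subject, for which the 42-day screening window leaves room; and lower ribavirin exposure in the few affected. It helps only subjects not yet dosed.
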